Dorgenmeltucel-L (HyperAcute Melanoma) immunotherapy consisting of equal cell doses of each of three allogeneic melanoma cancer cell lines engineered to express the murine  $\alpha(1,3)$ galactosyltransferase gene.

Dosage Treatment:

Arm 1 will receive either:

Arm 1A - ipilimumab at 3 mg/kg given every 3 weeks x 4 doses **or**

Arm 1B - nivolumab at 240 mg given every 2 weeks **or**

Arm 1C - pembrolizumab at 2 mg/kg given every 3 weeks **AND** 300 Million HAM cells per each immunization, given every week x 4, every 2 weeks for 5 months, every month for 6 months, and every 3 months x 4;

Arm 2 will receive either:

Arm 2A - ipilimumab at 3 mg/kg given every 3 weeks x 4 **or**

Arm 2B - nivolumab at 240 mg given every 2 weeks **or**

Arm 2C - pembrolizumab at 2 mg/kg given every 3 weeks

Clinical Endpoints:

1. Safety
2. Progression-free survival (PFS)
3. Overall response rate
4. Duration of objective response
5. Duration of stable disease
6. Overall survival (OS)
7. ████████████████████

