## 2.3 Clinical Experience of Dorgenmeltucel-L (HyperAcute Melanoma)

In the phase 1 dorgenmeltucel-L Trial NLG0104, 6 subjects received the melanoma immunotherapy. Six patients, 2 men and 4 women, mean age- 60 years (range, 36-76), were vaccinated with one priming dose of 500 million cells and up to eleven booster doses of

300 million cells. Observed events unrelated or unlikely to be related to the immunotherapy included Grade 1 fatigue, pruritus, nausea, vomiting, constipation, dysphagia, dermal change, facial edema, hyperglycemia, pain, and nocturia. Grade 1 events possibly related to the immunotherapy included fatigue, nausea, and dysgeusia. Grade 2 events unrelated or unlikely related to the immunotherapy include pruritus, cellulitis, left hemianopsia, and headache. One Grade 3 cellulitis was observed after a brown recluse spider bite in one of the subjects. Events probably or definitely related to the immunotherapy include Grade 1 and 2 injection site reactions to include redness, swelling, and itching. Five of the six patients went off study, 3 due to progression of disease and 2 due to concurrent illness. One subject remains on long-term follow-up with stable disease (> 5 years).

Riker *et al.* have since completed a phase 2 clinical trial of dorgenmeltucel-L (NLG12036, NewLink Genetics) combined with pegylated interferon (Sylatron™, Merck). Trial design consisted of a 12-week regimen with the initial 4 weekly treatments consisting of dorgenmeltucel-L alone (intradermally) followed by 8 additional treatments of dorgenmeltucel-L plus Sylatron™ (subcutaneously, 6 µg/kg). Trial endpoints include clinical response, overall safety and correlative findings for observed anti-tumor effect. They report a total of 25 patients accrued with a median age 60, 68% male with 21 patients completing the trial, 4 stopped due to progressive disease (PD).

By RECIST criteria, of 16 Stage IV patients, there were 2 complete responders (CR), 1 with stable disease (SD) and 4 with no evidence of disease (NED) after resection. For Stage III patients, 4/9 remains NED, 1 patient with slowly progressive disease with a single site resected and currently NED. The median overall survival is 29 months, with 60% of the patients surviving for >1 year and 12/25 (48%) still alive. All evaluable patients (21/21) seroconverted, developing autoimmune antibodies. Vitiligo developed in 4/25 patients, correlating with 2 CR and 2 NED.

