## **2.5 PD-1 Checkpoint Inhibitors (Nivolumab and Pembrolizumab)**

Two anti-programmed death 1 (PD-1) antibodies, nivolumab and pembrolizumab, were approved in 2014 by the Food and Drug Administration for the treatment of metastatic melanoma after progression during ipilimumab treatment and, in patients with BRAF-mutated melanoma, after progression during treatment with a BRAF inhibitor. These antibodies were associated with objective responses in 30 to 40% of patients. Two phase 3 trials have shown superior efficacy of nivolumab, as compared with chemotherapy, in previously untreated patients with wild-type BRAF tumors or in patients with either mutant or wild-type BRAF tumors after progression during ipilimumab therapy and, in patients with tumors positive for BRAF mutation, after progression during treatment with a BRAF inhibitor (Robert C, NEJM, 2015 and Weber JS, Lancet, 2015). Recently, pembrolizumab was associated with longer progression-free survival and overall survival and higher response rates than those associated with ipilimumab in a phase 3 trial involving patients with advanced melanoma (Robert C, NEJM, 2015).

In May 2015, results from the CheckMate 067 trial were presented. This study involving patients with previously untreated advanced melanoma, treatment with nivolumab alone or with the combination of nivolumab and ipilimumab resulted in significantly longer progression-free survival and higher objective response rates than did treatment with ipilimumab alone. The incidence of adverse events in this study was, in general, lowest in the nivolumab group and highest in the combination group.

Pembrolizumab was first evaluated in the large, phase 1 KEYNOTE-001 study (Robert C, Lancet, 2014). In a pooled analysis of 411 patients with advanced melanoma enrolled in KEYNOTE-001 and after a median follow-up duration of 18 months, the response rate was 34%, the response was maintained in 81% of those patients, and median overall survival was 25.9 months (Ribas A, 2014)

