### Duration of Response

Duration of overall response: The duration of overall response is measured from the time measurement criteria are met for CR or PR (whichever is first recorded) until the first date that recurrent or progressive disease is objectively documented (taking as reference for progressive disease the smallest measurements recorded since the treatment started).

Duration of stable disease: Stable disease is measured from the start of the treatment until the criteria for progression are met, taking as reference the smallest measurements recorded since the treatment started, including the baseline measurements.

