### New Lesion Measurement

The irRC are tumor assessment criteria that have been developed to better capture the activity of immunotherapeutic agents. These criteria have been used with success in clinical studies that were performed with ipilimumab in advanced metastatic melanoma and in lung cancer.

Additional tumor response data will be collected, beyond what is required to apply the RECIST criteria. More specifically, the investigator will have to record in the CRF the bi-dimensional measurements for each new lesion which has become measurable in each tumor assessment.

To support evaluation of progression-free survival based on irRC criteria (irPFS) in this indication, investigators must perform tumor assessments (including new lesion measurements) during the Toxicity/Progression Follow-up Phase in subjects who have experienced RECIST progression until the total sum of product diameters (SPD including new lesions) has increased 25% or more from the nadir or until subjects discontinue study therapy regardless of whether the subject is initiating subsequent therapy. All available post RECIST progression tumor imaging- based assessments during this phase in the study must be entered into the CRF, including any standard of care assessments and any assessments performed while under non-study subsequent cancer therapy.

Any subject who develops an objective tumor response (CR or PR) or progression (PD) is required to undergo confirmatory scans no less than 4 weeks since the prior scan in order to verify the reliability of the radiologic finding. Sites are encouraged to collect additional CT scans after RECIST PD has been confirmed, as long as a subsequent line of therapy has not been initiated.

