### **Efficacy Analyses**

The primary efficacy endpoint is PFS, where disease progression is defined according to RECIST v1.1. Progression free survival will be summarized using the Kaplan-Meier method of estimation, including the 25th, 50th, and 75th percentiles of time to progression with 95% confidence intervals. Kaplan-Meier plots will be produced by disease status strata to examine the difference in response rates between treatment groups. A stratified log rank test will be applied to test for treatment effect on PFS.

Overall response rate is defined as subjects with a best overall response of at least stable disease. Subjects' best overall response, as determined by the investigator from RECIST, will be summarized by presenting the numbers and percentages of subjects in each response category. The overall response rate will be summarized similarly. Ninety-five percent confidence intervals (CIs) will be constructed for the overall response rate.

The duration of overall response is measured from the time measurement criteria are met for CR or PR (whichever is first recorded) according to RECIST v1.1 until the first date that recurrent or progressive disease is objectively documented (taking as reference for progressive disease the smallest measurements recorded since the treatment started). Duration of overall response will be analyzed in a similar manner to PFS.

Duration of stable disease is measured from the start of the treatment until the criteria for progression are met according to RECIST v1.1, taking as reference the smallest measurements recorded since the treatment started, including the baseline measurements. Duration of stable disease will be analyzed in a similar manner to PFS.

Overall survival is defined as the time to death or last contact and will be summarized in a similar manner to PFS.

As additional secondary endpoints, analysis of PFS, overall response rate, duration of overall response, and duration of stable disease will be repeated using the irRC criteria to identify disease response.

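### The overall response rate counts stable disease, so it is a disease control rate under the wrong label; CR+PR has no planned interval, and the percentage rule conflicts with the all-randomised population

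*Combined protocol and SAP*

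**What the plan says.** **Rate.** Section 12.3, Efficacy Analyses: "Overall response rate is defined as subjects with a best overall response of at least stable disease". The only response proportion given an interval is this one: "Ninety-five percent confidence intervals (CIs) will be constructed for the overall response rate". The analysis "will be repeated using the irRC criteria to identify disease response".

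**Duration.** Section 9.1 (Duration of Response), repeated in Section 12.3, says that duration of overall response is "measured from the time measurement criteria are met for CR or PR". Duration of stable disease is a separate endpoint.

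**Sample size.** Section 12.1, describing the original response-rate design, gives the control arm a disease control rate of 22% and the combined arm a response rate of 42%, and treats the two as one quantity.

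**Who is counted.** Three provisions bear on the denominator:
- Populations to be Analyzed (12.3) makes the full analysis set (FAS), all randomised patients, the primary efficacy population.
- Statistical Methodology (12.3) shows a missing category in categorical tables but bases percentages on non-missing data.
- Definitions (9.1) limits evaluability for objective response to patients with measurable baseline disease, at least one cycle of therapy and a re-evaluation. Early objective progressors are kept.

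Missing Data (12.3) defers endpoint-specific imputation rules to the SAP. The supplied text contains no such rule for this endpoint.

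**The concern.** The word response carries two meanings within one section. A patient whose best result is stable disease counts as a responder in the rate but has no CR or PR from which to start a duration of response. A reader of the report would see a number of responders that disagrees with the number in the duration analysis. The rate could also be set beside the background figure in Section 2.5, "These antibodies were associated with objective responses in 30 to 40% of patients", which is a different quantity.

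The percentage rule adds a second problem. The trial is open-label and response is investigator-determined, so unequal numbers of unassessed patients in the two arms are plausible, although the documents do not quantify this. If unassessed patients leave the denominator, the arm that has more of them gets the higher rate for the same number of successes.

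No hypothesis test is planned for secondary endpoints, so the estimate and its interval are the whole output here. The label and the denominator therefore matter.

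**Working it through.** **1. The plan's own figure.** Inputs from Section 12.1: 22% versus 42%, 80% power, two-sided alpha 0.20, 1:1 allocation, 100 patients.

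n per arm = [z(0.90)·√(2·p̄·(1−p̄)) + z(0.80)·√(p1(1−p1) + p2(1−p2))]² / (p2−p1)², with p̄ = 0.32.

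= [1.2816·√0.4352 + 0.8416·√0.4152]² / 0.04 = (0.845 + 0.542)² / 0.04 = 48.1, so 49 per arm and 98 in total. At 50 per arm the power is 81.1%. The stated 100 reproduces. The calculation needs only two proportions, so it does not show whether they are CR+PR or CR+PR+SD. The documents do not split the 22% into CR, PR and SD, so a CR+PR control rate cannot be derived.

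**2. The definitions side by side.**

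| Best response | Counted in the rate (12.3) | Has a duration of response (9.1, 12.3) |
|---|---|---|
| CR | yes | yes |
| PR | yes | yes |
| SD | yes | no |
| Non-CR/non-PD, non-measurable disease only | not stated | no |

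The last row is open because Section 9.1 (patients with non-measurable disease) advises against calling that result stable disease. Counting one such patient or not moves the rate by 1/50 = 2.0 points in an arm of 50.

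**3. What the label changes, on the protocol's own data.** Section 2.3 reports 16 Stage IV patients with 2 CR, 1 SD and 4 with no evidence of disease after resection. No PR is mentioned and 0 is assumed. The regimen differed (with pegylated interferon). The exact (Clopper-Pearson) 95% limits for x of n are the 0.025 quantile of Beta(x, n−x+1) and the 0.975 quantile of Beta(x+1, n−x).
- CR+PR: 2/16 = 12.5% (1.6 to 38.3)
- At least SD: 3/16 = 18.8% (4.0 to 45.6)

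The shift is one patient and the intervals overlap widely. This illustrates the definition and does not predict this trial.

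**4. The non-missing rule.** Assumptions with no source in the documents: 50 patients and 15 successes in each arm, with u patients unassessed and treated as missing. Rate under the rule = 15/(50−u). Rate over all randomised = 15/50 = 30.0% whatever u is.

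| Unassessed, arm X vs arm Y | Rates under the rule | Difference (points) |
|---|---|---|
| 0 vs 0 | 30.0% vs 30.0% | 0.0 |
| 5 vs 5 | 33.3% vs 33.3% | 0.0 |
| 0 vs 5 | 30.0% vs 33.3% | 3.3 |
| 2 vs 8 | 31.25% vs 35.7% | 4.5 |
| 0 vs 10 | 30.0% vs 37.5% | 7.5 |

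Equal numbers unassessed raise both rates but create no difference between arms. Only imbalance does.

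**5. Patients with no apparent disease (NAD).** They are eligible (Section 3.1) and their stratum is not capped (Section 12.2). They belong to the FAS but fall outside the Section 9.1 evaluable set, and CR, PR and SD by target lesions do not apply to them. No provision says which rule governs this rate.

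**The case against.** **The quantity may be deliberate.** Section 12.1 already pairs a disease control rate with a response rate as if they were one. Section 9.1 also uses overall response as the heading for every category, including SD and PD. A reader might infer that everywhere else in the plan response means CR or PR, citing the requirement that "Any subject who develops an objective tumor response (CR or PR) or progression (PD) is required to undergo confirmatory scans" and the Synopsis endpoint "Duration of objective response". The documents do not support that. Both texts say objective response, the Synopsis lists overall response rate as a separate item, and Section 12.1 goes the other way. The contradiction rests on the duration definition in Sections 9.1 and 12.3. This part of the objection stands and shapes the remedy: keep the quantity, correct its name, and add CR+PR.

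**A denominator exists.** A reader might also infer that the plan gives none. It does: the FAS is the general efficacy population. What stands is narrower. The non-missing rule and the evaluable set are not reconciled with the FAS for this endpoint.

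**The illustrations are assumed.** This is true of both the unassessed counts and the 15 of 50. Unassessed patients might instead be reported as not evaluated, or as irUN under irRC, and not treated as missing; the plan does not say which.

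**The consequences are small.** Each response category is tabulated, so CR+PR and an interval can be worked out from the counts. The missing count is displayed, and no comparison with the 30 to 40% background figure is planned. This stands and limits the severity.

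**Conclusion.** The definition is wrong as written, and more than missing detail. Followed literally, the report presents a disease control rate as an overall response rate, its responders do not match the duration-of-response analysis, and CR+PR gets no planned interval. The conclusion on the label needs no assumption.

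The denominator point is a conflict between stated rules. Its size depends on how many patients go unassessed, how unevenly, and whether they are treated as missing. In the assumed scenarios the spurious difference runs from 0 to 7.5 points.

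The change should be made, but the impact is modest. The endpoint is secondary and untested, the category counts are reported, and neither the primary PFS analysis nor the current PFS sizing is affected. The documents do not support a claim that the disease control quantity itself is illegitimate or must be dropped.

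**What to change.** In Section 12.3, Efficacy Analyses, and in the SAP:

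1. Rename the CR+PR+SD rate disease control rate and keep it, with its 95% CI.
2. Add an objective response rate, CR+PR by RECIST 1.1, with a 95% CI.
3. Use the FAS as the main denominator for both. Keep unassessed patients in it as non-responders and exempt these rates from the non-missing percentage rule.
4. Add a supportive row on the Section 9.1 evaluable set (measurable baseline disease), which excludes NAD patients.
5. State whether non-CR/non-PD counts toward disease control.
6. State the matching irRC rule separately. Section 9.1 defines irSD as any evaluable result that is not irCR, irPR or irPD, so the RECIST wording does not carry over.

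**Cost.** A short text edit and one or two table rows, with no new data or patients. The figure called response rate will generally be lower (in the Section 2.3 example, 12.5% in place of 18.8%). Counting unassessed patients as non-responders is conservative, and NAD patients in the FAS cannot achieve CR or PR; the supportive row lets a reader see the effect of both.

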**Multiplicity Issues**

No adjustments for multiple comparisons are required for the primary efficacy analysis, since a single primary outcome variable has been specified. No formal hypothesis testing will be applied to the secondary efficacy endpoints.

**Missing Data**

In general, there will be no substitutions made to accommodate missing data points. All data recorded on the case report form will be included in data listings that will accompany the clinical study report. For analysis of time to event endpoints, subjects who have no efficacy evaluations will be considered censored at time 0. Imputation rules for specific efficacy endpoints will be detailed in the statistical analysis plan.

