### **Methods for Evaluation of Measurable Disease**

All measurements should be taken and recorded in metric notation using a ruler or calipers. All baseline evaluations should be performed as closely as possible to the beginning of treatment and never more than 4 weeks before the beginning of the treatment.

The same method of assessment and the same technique should be used to characterize each identified and reported lesion at baseline and during follow-up. Imaging-based evaluation is preferred to evaluation by clinical examination unless the lesion(s) being followed cannot be imaged but are assessable by clinical exam.

Clinical lesions: Clinical lesions will only be considered measurable when they are superficial (*e.g.*, skin nodules and palpable lymph nodes) and  $\geq 10$  mm diameter as assessed using calipers (*e.g.*, skin nodules). In the case of skin lesions, documentation by color photography, including a ruler to estimate the size of the lesion, is recommended.

Chest x-ray: Lesions on chest x-ray are acceptable as measurable lesions when they are clearly defined and surrounded by aerated lung. However, CT is preferable.

Conventional CT and MRI: This guideline has defined measurability of lesions on CT scan based on the assumption that CT slice thickness is 5 mm or less. If CT scans have slice thickness greater than 5 mm, the minimum size for a measurable lesion should be twice the slice thickness. MRI is also acceptable in certain situations (*e.g.* for body scans).

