**For Patients with Measurable Disease (i.e., Target Disease)**

Target Lesions	Non-Target Lesions	New Lesions	Overall Response	Best Overall Response when Confirmation is Required*
CR	CR	No	CR	≥4 wks. Confirmation**
CR	Non-CR/Non-PD	No	PR	≥4 wks. Confirmation**
CR	Not evaluated	No	PR	
PR	Non-CR/Non-PD/not evaluated	No	PR	
SD	Non-CR/Non-PD/not evaluated	No	SD	documented at least once ≥4 wks. from baseline**
PD	Any	Yes or No	PD	no prior SD, PR or CR
Any	PD***	Yes or No	PD	
Any	Any	Yes	PD	

\* See RECIST 1.1 manuscript for further details on what is evidence of a new lesion.

\*\* Only for non-randomized trials with response as primary endpoint.  
 \*\*\* In exceptional circumstances, unequivocal progression in non-target lesions may be accepted as disease progression.

Note: Patients with a global deterioration of health status requiring discontinuation of treatment without objective evidence of disease progression at that time should be reported as “*symptomatic deterioration.*” Every effort should be made to document the objective progression even after discontinuation of treatment.

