### **Populations to be Analyzed**

The primary population for efficacy will be the full analysis set (FAS), defined as all randomized subjects. In the FAS patients will be analyzed in the treatment group to which they were assigned.

The primary population for safety analyses will be the safety analysis set, defined as all randomized subjects who receive at least one administration of study treatment (dorgenmeltucel-L or immune checkpoint therapy).

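### The time-0 censoring rule makes no exception for death, and Section 12.3 never makes death a PFS event, so known early deaths can drop out of the primary analysis

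*Combined protocol and SAP*

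**What the plan says.** Section 12.3, Missing Data, sets one rule for every time-to-event endpoint: "For analysis of time to event endpoints, subjects who have no efficacy evaluations will be considered censored at time 0". The same paragraph then defers detail: "Imputation rules for specific efficacy endpoints will be detailed in the statistical analysis plan". The supplied text contains no such endpoint-specific rule.

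Section 12.3, Efficacy Analyses, defines only the progression half of the primary endpoint: "The primary efficacy endpoint is PFS, where disease progression is defined according to RECIST v1.1". It labels the Kaplan-Meier percentiles as time to progression, and Section 12.1 also states the control-arm assumption as a median time to disease progression. Death is named only for the secondary endpoint: "Overall survival is defined as the time to death or last contact and will be summarized in a similar manner to PFS".

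The analysis population is not restricted by assessment: "The primary population for efficacy will be the full analysis set (FAS), defined as all randomized subjects". Section 9.1 puts tumour assessments about every three months, and the protocol schemas place the first after Week 12 (Arm 2) or Week 14 (Arm 1). Section 8 requires survival checks at least every three months, so death dates will be available.

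**The concern.** A patient censored at time 0 is in no risk set. Keeping such a patient in the full analysis set is a formality, because the log-rank statistic and the Kaplan-Meier curve are the same as if the patient had been deleted. If the patient was deleted because of death before the first scan, the censoring is informative: the worst outcomes leave the primary endpoint, and PFS is overstated.

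Other text narrows the gap without closing it. Caliper assessment could catch some early progressions, but "Clinical lesions will only be considered measurable when they are superficial". A patient who declines and stops treatment "without objective evidence of disease progression at that time should be reported as" symptomatic deterioration, which is not RECIST progression. The instruction that follows ("Every effort should be made to document the objective progression even after discontinuation of treatment") cannot be carried out once the patient has died.

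At stake is whether the primary test can see a difference in early deaths, in either direction. If the combination arm had more of them, part or all of the excess would be missing from the test. If it had fewer, part or all of that benefit would be.

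**Working it through.** **1. The plan's own event count.** Inputs from Section 12.1: 1:1 allocation, two-sided alpha 0.20 (z = 1.2816), 96 events, HR 0.6895 at 70% power and HR 0.6435 at 80%.

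Freedman: d = ((1 + HR)/(1 − HR))² × (z_α/2 + z_power)².
- HR 0.6435: (1.6435/0.3565)² × (1.2816 + 0.8416)² = 21.25 × 4.51 = 95.8, so 96.
- HR 0.6895: (1.6895/0.3105)² × (1.2816 + 0.5244)² = 29.61 × 3.26 = 96.6, so 97.

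The stated 96 is reproduced.

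**2. Time-0 censoring equals deletion.** In one simulated data set of 100 patients with 10 early deaths, the log-rank chi-square was 0.561 with those deaths censored at time 0, 0.561 with them deleted, and 0.133 with them counted as events.

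**3. How many patients.** The documents give no early-death rate for this trial. Section 2.5 cites one-year survival of 58.2%, 68.4% and 74.1% in a randomised trial of ipilimumab and pembrolizumab. Assuming a constant hazard, P(death before Day 91) = 1 − S^(91/365.25):
- 58.2%: 0.126
- 68.4%: 0.090
- 74.1%: 0.072

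The share of these deaths with no tumour assessment is unknown, so three values are shown. The last column assumes that only half the enrolled patients carry this hazard and the rest have no early death, because resectable and resected patients also enrol.

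| Share unassessed | Affected per 100, all at this hazard | Affected per 100, half at this hazard |
|---|---|---|
| 25% | 1.8 to 3.2 | 0.9 to 1.6 |
| 50% | 3.6 to 6.3 | 1.8 to 3.2 |
| 100% | 7.2 to 12.6 | 3.6 to 6.3 |

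**4. Event target and power.** With exactly 100 randomised, k affected patients leave at most 100 − k events, so 96 is out of reach once k is 5 or more. The binomial probability of 5 or more is 3–21%, 29–76% and 85–99.7% for the three shares, or 0.2–2%, 3–21% and 29–76% in the half-hazard case. The power cost is modest. By Schoenfeld, power = Φ(√d/2 × |ln HR| − 1.2816). At HR 0.6435:
- d = 96: Φ(4.899 × 0.4408 − 1.2816) = Φ(0.878) = 81.0%
- d = 87 (13 patients lost): Φ(4.664 × 0.4408 − 1.2816) = Φ(0.774) = 78.1%

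Freedman gives 80.1% and 77.1%.

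**5. What the test can see.** Simulation: 50 per arm, median progression 3 months in both arms, early deaths uniform over 0–3 months, administrative censoring at 24 months, 30,000 replicates. The result is the share of trials with z > 1.2816 against the arm with more early deaths. Early deaths that had a tumour assessment count as events at death. The arm splits are assumptions; 13% v 7% is a stress case.

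| Early deaths | Progression dating | All deaths counted | 25% unassessed | 50% | 100% |
|---|---|---|---|---|---|
| 13% v 7% | at scans | 20.1% | 17.7% | 15.3% | 10.5% |
| 13% v 7% | continuous | 15.1% | 14.3% | 13.4% | 11.9% |
| 11% v 9% | at scans | 13.0% | 12.5% | 11.9% | 10.4% |
| 11% v 9% | continuous | 11.7% | 11.5% | 11.3% | 10.8% |

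With 10% in each arm, every version gives 10.2–10.4%, so the rule does not bias the test when early deaths are equal.

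If the text is taken literally and death is never a PFS event, the scan-dated 13% v 7% case gives about 10% at every unassessed share. On that reading the test cannot see the excess at all.

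**The case against.** The strongest reply is that the reading is not forced. Efficacy evaluations is undefined. In the study calendars, the heading for evaluations covers every row, including consent and vital signs, and the tumour row is also marked at baseline. The rule covers all time-to-event endpoints, the protocol classes OS as efficacy, and survival status could therefore count as an efficacy evaluation, in which case a recorded death takes the patient out of the rule. The name progression-free survival conventionally includes death. The SAP may supply the missing rule.

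The ambiguity is real, and it is why confidence is medium. It does not remove the problem. If baseline rows or survival status counted, almost no followed patient would lack an evaluation and the rule would have little left to do. For a RECIST endpoint, tumour assessment is the natural sense, and Section 9.1 uses re-evaluation of disease in that sense. Even if death is meant to be an event, an explicit censoring rule with no exception would still govern an unassessed death. The SAP rule is promised but not supplied.

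A second reply is that the sizes rest on assumption. This is correct: the unassessed shares and arm splits have no source in the documents, and the hazard comes from another trial. This trial also enrols resectable and resected patients and excludes active CNS metastases. Nor should the 96-event point carry much weight. A target of 96 from 100 leaves little room for any censoring, and Section 12.1 speaks of 100 evaluable patients, which might allow more than 100 to be randomised. The Synopsis says 100 randomised.

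A third reply is that two issues are joined: death not being named as an event, and the time-0 rule. The partial-share simulation figures do presuppose that assessed deaths count. Taking the first issue literally makes the loss larger, and the same sentences repair both.

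Finally, the deaths remain in the safety listings and should be in OS. That is so, but neither is the primary test.

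**Conclusion.** The concern holds. As written, and on the natural reading of the undefined term, patients known to have died before any post-baseline tumour assessment contribute nothing to the primary PFS comparison, although they belong to its analysis population. No supplied text overrides this. The wording does not exempt OS either, although the OS definition and the survival checks suggest OS was not meant.

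The probable size is a few patients per 100, with 7 to 13 as an upper bound if every patient carries the cited hazard and no early death was assessed. The power loss is at most about 3 points and is not the main reason to act. The reason is informative censoring in an open-label trial: with unequal early deaths the rule hides part of the difference, and all of it in the worst case. With equal early deaths the log-rank test is unaffected and PFS is only slightly overstated. This should be fixed before analysis; confidence is medium because the term is undefined and the deferred rules are not available.

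**What to change.** In Section 12.3 and the SAP:

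- Define PFS as the time from randomisation to the first RECIST 1.1 progression or death from any cause.
- Count a death with no post-baseline tumour assessment as a PFS event on the date of death.
- Replace the undefined term with post-baseline tumour assessment, and limit time-0 censoring to patients who have none and are not known to have died.
- State that OS uses the date of death, or the date last known alive, whether or not tumour assessments exist.

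The cost is three or four sentences. Deaths and survival status are already collected, so no new data are needed.
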